### 5.3. Duplex ultrasound scan

Duplex ultrasound scans will be performed by two blinded experts based at different clinical centers. At Center 1, all investigations will be done with MyLab30 (Esaote, Italy) using a linear transducer with a frequency of 5–13 MHz. At Center 2, Voluson I (General Electric, USA) with a linear transducer frequency of 5–13 MHz will be used. All veins of the calf and thigh should be observed during every DUS.

Examinations should be performed in a horizontal position: the common femoral (CFV), the femoral vein (FV), the great saphenous vein (GSV) and its tributaries should be evaluated in the supine position with light bending in the knee joint. The popliteal vein (PV), small saphenous vein (SSV), and its branches should be examined in the prone position. If it is not possible to move the patient or the patient is unconsciousness, the PV

and SSV may be observed during leg supination and bending in the knee joint by ~45 degrees. The posterior tibial veins (PTV) and the medial group of the calf muscle veins should be examined in the supine position with the supinated and slightly bent in the knee joint leg. The peroneal veins (PeV) and lateral calf muscle veins should be examined in the supine position with pronated and knee bent at 45–90 degrees leg. The anterior tibial veins (ATV) should be investigated in the supine position with an unbent knee. In case of any problems with calf vein visualization, the examination should be repeated in the sitting position with the leg bent in the knee joint at 45 degrees.

The main criterion for vein patency is compressibility in the B-mode. If it is necessary, the color flow mode may be used to reveal blood flow in the target vein with the stimulation by manual compression or active movements in the ankle joint. Iliac veins and IVC should be observed in case of clinical suspicion of their thrombosis using convex transducer with the frequency of 2.5–5 MHz.

During the primary DUS, it is obligatory to document all post-thrombotic vein changes, such as residual venous obstruction and valve insufficiency, and their localization in patients with a personal history of DVT. The re-occlusion of the previously affected vein revealed during DUS follow-up must be considered as a new DVT. However, any changes in the degree of residual venous obstruction should not be considered.

Besides venous investigation, the ABI at the posterior tibial artery should be measured using the pulsed wave Doppler method in all screened patients.

#### **5.4. Examination during inpatient treatment**

The following data on surgical procedure should be obtained from the medical records after intervention: the surgical profile (e.g., abdominal, thoracic, neck, pelvis, cranial), type of surgery (open, endoscopic, endoscopy assisted), urgency of surgery (emergent = performed in 0–2 h after admission, urgent = performed in 0–6 days after admission, elective = performed independently at the time of admission), radicalism of surgery (radical, palliative), type of anesthesia (general, regional, combined), surgery duration, blood loss, and intraoperative infusion.

The routine clinical examination of the patient will be performed in a daily manner with special attention to the possible complications, such as DVT, SVT, PE, bleeding, and leg skin injury. IPC sleeves should be removed for 15–20 mins every day for skin inspection and investigation of pedal pulsation. Consultation of any relevant specialist

(cardiologist, neurologist, pulmonologist, infections) should be performed if any complication or development of new co-morbidity will be observed during the follow-up.

DUS should be performed every 3–5 days after surgery and in emergency manner if any clinical suspicion for DVT or SVT appeared. In an emergency manner, DUS may be performed by a blinded expert or specialist on duty on weekend and holidays. However, all conclusions of non-investigational medical staff must be verified by a blinded expert.

SPECT/CT or CTPA should be used to verify PE in an emergency manner if clinical suspicion appeared. An autopsy must be performed in all died patients to verify the absence of DVT and PE.

In case of any clinical suspicion for a VTE event, IPC should be interrupted until final verification of the diagnosis. In the case of positive DUS, CTPA, and SPECT/CT, the therapeutic anticoagulation should be prescribed, and IPC should be removed. In the case of clinical suspicion for VTE with negative results of instrumental tests, IPC should not be returned until the proper diagnosis that mimics VTE will be found.

Any revealed leg skin lesion should be judged individually for the possibility to continue ECS and IPC application. If the decision will be made to stop IPC, the patient should be withdrawn from the study according to the protocol.

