### **3.4. Protocol deviations**

The serious protocol deviations that required patient exclusion from the final analysis are: missed two or more scheduled DUS; missed the final scheduled DUS before discharge; autopsy rejected; inability to assess compliance with IPC (no information in the Compliance sheet); gross inconsistencies between source documentation and an CRF; violations of the procedure for obtaining informed consent; failure to follow the procedures of the trial protocol; the inability to collect all the data used in evaluating the final goals of the study (for example, the lack of records in the source documentation necessary to verify the inclusion/exclusion criteria, safety, and efficiency criteria); any other protocol deviations considered as significant.

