### **3.5. Endpoints and definitions**

**Primary endpoint:** asymptomatic venous thrombosis of the lower limbs detected by DUS during inpatient treatment.

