## 8. Statistical analysis plan and sample size calculation

**Statistical analysis plan.** The primary statistical analysis is designed as intention-to-treat with the use of two-tailed Fisher's exact test to compare the primary endpoint between two groups. The primary endpoint will be reported as an absolute number, percentage, and relative risk with 95% CI. Secondary statistical analysis of the primary endpoint will be made using an unadjusted Cox proportional-hazards model. The data will be censored on the time of VTE registration, or death, or discharge from the hospital and reported as a hazard ration with 95% CI. Kaplan-Meier curves will be used to compare time-to-event distribution. Cox proportional-hazards models adjusted for the clinical center, surgery profile, type of surgery, emergency of surgery, type of anesthesia, surgical radicalism, malignant disorder, Caprini score, and time to start LMWH injections will be used.

A similar analysis for the per-protocol population, but that excluded patients with gross violations of the protocol and premature discontinuation of at least one component of combined prophylaxis (ECS, IPC or LMWH), will be performed for the primary endpoint.

Secondary endpoints will be analyzed with two-tailed Fisher's exact test and will be represented as an absolute number, percentage, and relative risk with 95% CI.

Cox proportional-hazards models will be used for the prespecified subgroup analysis for the following subgroups: surgical profile; type of surgery; the urgency of surgery; the radicalism of surgery; type of anesthesia; malignant or benign disorder; preoperative, postoperative, or delayed start of LMWH injections; and pre-operative or post-operative IPC application.

Sensitivity analysis will address to the per-protocol analysis, compliance with IPC (restricted for 90% and more), duration of follow-up (restricted to 7 days and more), and the number of postoperative DUS (restricted with two and more).

Missing data on the primary endpoint are not anticipated in the inpatient settings, so no analysis for missing data being planned.

Adjusting for multiple comparisons and imputation for missing values will not be performed. The 95% confidence intervals will be not adjusted for multiplicity, and therefore, inferences drawn from these intervals might be not reproducible. The interim analysis is not planned.

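### The inpatient scan schedule can leave up to 4 days before discharge unexamined, the analysis treats those days as observed event-free, and section 3.4 excludes patients on a final scan that section 5.4 does not define

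*Combined protocol and SAP*

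**What the plan says.** All places are in the combined protocol and SAP.

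- **Endpoint (section 3.5).** The primary endpoint is "asymptomatic venous thrombosis of the lower limbs detected by DUS during inpatient treatment". In a patient who leaves hospital alive it can be recorded only if a scan finds it.
- **Schedule (section 5.4).** "DUS should be performed every 3–5 days after surgery and in emergency manner if any clinical suspicion for DVT or SVT appeared". This is the only inpatient schedule in the text, and it names no scan at or near discharge.
- **Exclusions (section 3.4).** "The serious protocol deviations that required patient exclusion from the final analysis are: missed two or more scheduled DUS". The next item on that list is a patient who "missed the final scheduled DUS before discharge".
- **Primary analysis (section 8).** "The primary statistical analysis is designed as intention-to-treat with the use of two-tailed Fisher's exact test".
- **Time-to-event analysis (section 8).** "The data will be censored on the time of VTE registration, or death, or discharge from the hospital". The end of follow-up is discharge, not the last negative scan.
- **Missing data (section 8).** "Missing data on the primary endpoint are not anticipated in the inpatient settings, so no analysis for missing data being planned".
- **Sensitivity analyses (section 8).** One restricts on "the number of postoperative DUS (restricted with two and more"); the others are the per-protocol analysis and restrictions on IPC compliance and on length of follow-up. None uses the time from last scan to discharge.

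**The concern.** Two things do not fit together.

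First, the period over which the endpoint can be seen ends at the last scan, while the period over which patients are analysed ends at discharge. A silent thrombosis that starts between the two is a non-event in the Fisher test and is censored event-free at discharge in the Cox model. Nothing else in the plan recovers it for the primary endpoint. Scans on suspicion need symptoms, autopsy covers only deaths (section 5.4), and a thrombosis first seen at day 30 or 180 feeds a secondary endpoint, at a contact that may be a telephone call (section 5.5).

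Second, section 3.4 makes exclusion depend on a scan that section 5.4 does not identify. Two centers could classify the same patient differently. If the exclusion is applied to the primary analysis, that analysis is no longer intention-to-treat.

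At stake are under-counted events and, if scan timing or stay differs by arm, a relative risk that partly reflects how long patients were looked at.

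**Working it through.** **1. The plan's own figure.** Inputs from section 8: 30% vs 12%, two-sided alpha 0.05, power 80%, equal arms.
- Without continuity correction: n = [1.96·√(2·0.21·0.79) + 0.842·√(0.30·0.70 + 0.12·0.88)]² / 0.18² = 79.2, so 80 per arm.
- With continuity correction: (79.2/4)·[1 + √(1 + 4/(79.2·0.18))]² = 90 per arm, as stated. Enumerated two-sided Fisher power at 90 per arm is 81.2%.
- Allowance: 180/0.9 = 200, doubled to 400. Less 10%, this leaves 360, or 180 per arm.

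**2. Length of the unscanned period.** Scan every k days from surgery and discharge on day L. The gap is L mod k. Shortest stay taken as 7 days, from the minimum in-hospital LMWH period in section 4.2 (an assumption about stay).

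| Interval | Gap, discharge day 7 | Day 8 | Day 9 | Maximum, any L ≥ 7 |
|---|---|---|---|---|
| 3 days | 1 | 2 | 0 | 2 |
| 4 days | 3 | 0 | 1 | 3 |
| 5 days | 2 | 3 | 4 | 4 |

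At the 5-day interval a patient leaving on day 7, 8 or 9 has one scheduled scan and 2/7 = 29%, 3/8 = 38% or 4/9 = 44% of the stay unexamined. The gap is just under 5 days if the patient leaves on a scan day before the scan.

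**3. Share of in-hospital thromboses starting after the last scan.** The documents give neither stay nor onset pattern, so this is a range. Assumptions: interval drawn from 3, 4 or 5 days; thrombosis visible from onset.

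| Onset pattern | 7-day stay | 10-day stay | 14-day stay |
|---|---|---|---|
| Uniform | 27% | 15% | 11% |
| Front-loaded, mean 7 days | 19% | 8% | 4% |
| Front-loaded, mean 4 days | 14% | 5% | 2% |

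**4. Equal loss in both arms.** If a share m is missed in each arm, RR = 0.12(1−m) / [0.30(1−m)] = 0.40 for every m. Exact Fisher power:

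| Missed | Rates | 90 per arm | 180 per arm |
|---|---|---|---|
| 0% | 30% vs 12% | 81.2% | 98.6% |
| 10% | 27% vs 10.8% | 75.3% | 97.3% |
| 20% | 24% vs 9.6% | 68.5% | 94.9% |

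**5. Unequal scan timing, no true effect.** Take 30% in both arms, discharge on day 7, uniform onset, every control patient scanned on days 3 and 6, every IPC patient on day 5. Observed rates are 0.30·6/7 = 25.7% and 0.30·5/7 = 21.4%, so RR = 0.83. The Fisher test rejects 13% of the time at 180 per arm and 7.5% at 90, against just under 4% at either size with equal detection.

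This is an extreme split. Keeping it but discharging on day 10, the last scans fall on days 9 and 10 and the ratio reverses to 10/9 = 1.11. On days 15–17 both arms were last scanned on day 15 and the ratio is 1. Averaged over stays of 7–14 days at 180 per arm:
- uniform onset: RR 0.86, rejection 10%;
- front-loaded, mean 7 days: RR 0.92, rejection 6.1%;
- front-loaded, mean 4 days: RR 0.95, rejection 4.8%.

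**6. Sections 3.4 and 5.4 side by side.** A patient scanned on days 3 and 7 and discharged on day 11 has kept to section 5.4, since the next scan is due between days 10 and 12. If section 3.4 means a discharge scan, this patient is excluded. If it means the last scan of the series, the patient is analysed as event-free with 4 days unexamined.

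**The case against.** Most of the case on the other side concerns stronger readings, and against those it succeeds.

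- **A reader might infer that sections 3.4 and 5.4 contradict each other.** They need not. The only schedule is the 3–5-day series, so the final scheduled scan can naturally be read as its last member. What stands is an ambiguity, and the gap remains on that reading. The design figure is not shown and might settle it; this point rests on the text.
- **A reader might infer that staff who know the arm choose the scan days.** No section says who sets them. Section 5.3 has blinded experts perform the scans, and section 3.1 denies them the allocation list. Differential timing is a possibility left open, not a documented fact.
- **A reader might infer that the trial is underpowered.** The 30% comes from the team's previous observations of asymptomatic thrombosis, which must themselves have been detected under some scan schedule. Scaling it down may count the same loss twice. Even if it is scaled down, power at 180 per arm holds; the fall to 75% or 69% applies at 90 per arm, the size the doubling was meant to give each LMWH-timing subgroup.
- **A reader might infer from the two-scan sensitivity analysis that the plan expects patients to go home after one scan.** It need not: a patient positive on the first scan is withdrawn (section 3.3), and an early death may also leave one scan.
- **Exclusion from the final analysis might mean only the per-protocol analysis.** That would remove the conflict with intention-to-treat, but section 3.4 does not say so, and the sample-size paragraph allows 10% for losses that include protocol deviations, as if those patients leave the main comparison.

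The day-30 scan is partial mitigation, but for a secondary endpoint only. Against the claim as limited here, none of this closes the gap before discharge or makes it visible in the planned output.

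**Conclusion.** The point holds in a limited form. Section 5.4 allows up to 4 unscanned days before discharge, and section 8 treats them as observed. The exclusion in section 3.4 is ambiguous against section 5.4 and, as written, conflicts with the intention-to-treat primary analysis.

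The certain consequence is under-counting of events. Its size depends on stay and onset, which the documents do not give: 2% to 27% of in-hospital thromboses across the assumptions tried. If the loss is equal by arm, the relative risk is unaffected and whole-trial power stays at about 95% or more.

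Bias arises only if scan timing or stay differs by arm. The documents do not show that it will. They give some reason not to assume equality: the trial is open-label, no scan days are fixed, and section 1 reports that IPC devices tend to keep patients in bed and delay discharge. The 13% rejection rate is a corner case and should not be quoted as the expected error. The practical weakness is that no planned table or analysis would reveal a difference if it occurred.

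**What to change.** 1. **Sections 3.4 and 5.4.** State which scan is the final one. Within the existing 3–5-day window, use the same scan-day rule in both arms and place the last scan as near discharge as the window allows. Stays of 7 days or more can be built from 3-, 4- and 5-day steps (7 = 3+4, 8 = 4+4, 9 = 4+5, 11 = 3+4+4), so when discharge is foreseen at the previous scan no scan outside the window is needed. A gap will remain after unplanned discharges.
2. **Section 3.4.** Make a missed final scan an exclusion from the per-protocol set only.
3. **Section 8, reporting.** Tabulate by arm the number of postoperative scans and the days from last scan to discharge.
4. **Section 8, sensitivity.** Repeat the time-to-event analysis of the primary endpoint with follow-up ending at the last scan, by censoring there or by an interval-censored model.

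The cost is minor scheduling effort, one table and one extra analysis. A compulsory additional scan shortly before discharge would close the gap more fully, but it is arguably an added procedure and is not needed for this recommendation.

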### **5.5. Examination during outpatient treatment**

After discharge, patients should be evaluated at 30 and 180 days after surgery. The target content of examination should include DUS and clinical examination. However, it is allowed to make a phone call to interview the patient about his status and any new symptomatic VTE events.

During the clinical examination, the investigator should revise the patient's medical records for any symptomatic or asymptomatic VTE episodes, confirmed by appropriate radiological tests.

DUS in the outpatient settings should be performed by a blinded expert using the same methodology. Any new postthrombotic change (residual venous obstruction, valvular insufficiency) revealed on the 30th or 180th day of observation and had not been documented previously should be considered as a new venous thrombosis corresponding with the secondary endpoint.

If the patient would not be available for head-to-head examination, the phone call should be made, and the subject should be interviewed with special attention to possible

clinical signs of symptomatic VTE episode. If the patient will report a VTE episode confirmed by an appropriate test, he should be asked to send the medical records on this issue by e-mail. If the investigator would find that a patient had died, he should to gather appropriate documentation, confirming the cause of the lethal outcome.

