### **5.1. Baseline examination**

The screening examination is designed to assess patient's eligibility with the inclusion/exclusion criteria. The baseline examination will be performed a day before the surgery in case of elective surgery or just before or within 12 h after the urgent surgery. The basal examination contains the standard diagnostic procedures with special attention to the individual risk factors for postoperative VTE. Patients (or their representatives in case of unconsciousness or deep dementia) should be interviewed for the personal and family VTE history, any obstetrics complications, use of contraceptive pills or other estrogen-containing drugs, and current or previous malignant disorders. Lower limbs should be evaluated for the varicose veins and edema, skin and soft tissue infection, any skin lesions, and pedal pulsation. The relevant co-morbidities, such as congestive heart failure (CHF), chronic obstructive pulmonary disease (COPD), serious lung disease or pneumonia, inflammatory bowel disease, sepsis, lower limb paralysis, and stroke should be evaluated and confirmed according to the medical records and involving other specialists. BMI will be calculated with the data from medical records.

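### Pre-existing venous reflux can be counted as a new thrombosis at day 30 or 180, because a baseline record of valve insufficiency is required only in patients with a DVT history

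*Combined protocol and SAP*

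**What the plan says.** Section 5.5 defines the outpatient event for every patient scanned after discharge. "Any new postthrombotic change (residual venous obstruction, valvular insufficiency) revealed on the" day-30 or day-180 scan that "had not been documented previously should be considered as a new venous thrombosis" and counts toward the secondary endpoint. Valvular insufficiency is listed beside residual obstruction, so either finding can qualify.

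Section 5.3 sets the baseline record against which a finding would be called new. At the primary duplex scan (DUS) it is obligatory to document post-thrombotic changes such as "residual venous obstruction and valve insufficiency, and their localization in patients with a personal history of DVT". No section requires the same record in other patients.

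The scan method in Section 5.3 is built around occlusion: "The main criterion for vein patency is compressibility in the B-mode", with color flow as an optional addition. No reflux test or reflux threshold is described. Section 5.5 carries this over: "DUS in the outpatient settings should be performed by a blinded expert using the same methodology".

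Section 5.1 asks for a clinical look at the legs: "Lower limbs should be evaluated for the varicose veins and edema". Section 3.5 defines distal, proximal and superficial thrombosis by incompressibility, occlusion or re-occlusion, and does not mention reflux.

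**The concern.** The event rule asks whether reflux was documented before, but for patients without a DVT history nobody is required to have looked for it. An empty record in those patients does not show that the valve was competent. Reflux present before surgery can then be read at day 30 or 180 as thrombosis that occurred after it.

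The population makes this plausible. Patients are over 40. Varicose veins and swollen legs each score a Caprini point. Section 3.2 names CVD, which the abbreviation list expands as chronic venous disease, among the conditions that may bring a patient to the entry threshold.

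At stake are the 30- and 180-day composites of symptomatic and asymptomatic venous thrombosis and symptomatic PE, which are the trial's evidence on thrombosis after discharge. Events unrelated to treatment would inflate the reported rates in both arms and understate any benefit of intermittent pneumatic compression (IPC).

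**Working it through.** **Step 1: the two rules side by side.**

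| | Patients with DVT history | Patients without DVT history |
|---|---|---|
| Valve insufficiency recorded at primary DUS (5.3) | Obligatory | Not required, not forbidden |
| Undocumented post-thrombotic valvular insufficiency at day 30/180 (5.5) | New thrombosis | New thrombosis |
| Criterion separating primary or old reflux from new post-thrombotic reflux | None stated | None stated |

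The gap is in the right-hand column: the event rule applies, but the record it depends on is not required.

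**Step 2: the plan's own figure.** Section 8 assumes 30% in controls and a 60% relative reduction, so 12% with IPC and a difference of 18 points, with two-sided alpha 0.05 and power 80%. The normal-approximation sample size with p̄ = 0.21 is

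n = [1.96·√(2·0.21·0.79) + 0.842·√(0.30·0.70 + 0.12·0.88)]² / 0.18² ≈ 79.2, that is 80 per arm.

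The continuity correction, (n/4)·[1 + √(1 + 4/(n·0.18))]², gives 90 per arm, as stated. Exact power of Fisher's test at 90 per arm is 81.2%. Then 180/0.90 = 200, as stated, and doubling gives 400, or 200 per arm. All of this concerns the inpatient primary endpoint, which does not use reflux, so no design figure changes.

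**Step 3: illustration of the dilution.** The documents give neither the prevalence of pre-existing reflux nor an expected rate for the outpatient composites. The inpatient planning rates are borrowed here only to show direction and scale. Let f be the share of truly event-free patients who are miscounted, equal in both arms:

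observed rate = p + (1 − p)·f; relative risk (RR) = observed IPC rate / observed control rate.

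| f (assumed) | Control, p = 0.30 | IPC, p = 0.12 | Difference | RR |
|---|---|---|---|---|
| 0 | 30.0% | 12.0% | 18.0 points | 0.40 |
| 5% | 0.30 + 0.70·0.05 = 33.5% | 0.12 + 0.88·0.05 = 16.4% | 17.1 points | 0.49 |
| 10% | 37.0% | 20.8% | 16.2 points | 0.56 |
| 20% | 44.0% | 29.6% | 14.4 points | 0.67 |

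At 200 per arm with everyone scanned, f = 10% means 200·0.70·0.10 = 14 false events in controls and 200·0.88·0.10 ≈ 18 with IPC.

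The dilution is stronger if the true rates are lower. With half the planning rates, 15% vs 6% (also an assumption), the RR becomes 0.56, 0.66 and 0.78 at f = 5%, 10% and 20%.

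**Step 4: what f contains.** It is not the prevalence of reflux. It is roughly the share with undocumented pre-existing reflux, times the share who have a DUS rather than a phone call, times the share in whom reflux is looked for and judged post-thrombotic. None of these is given, and each of the last two can only lower f.

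**The case against.** The strongest reply is that Section 5.5 does not count every undocumented reflux. The change must be new and post-thrombotic, so primary reflux or varicose disease does not qualify on a plain reading. A reader might infer that any patient with chronic reflux and no DVT history automatically meets the event definition. The text does not support that. What stands is narrower: the plan gives no way to tell post-thrombotic from primary reflux, so misclassification is possible. The word also gives no protection where reflux follows an old, unrecognised thrombosis, which is post-thrombotic and undocumented but not new.

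Second, Section 5.3 sets a minimum. It does not bar recording reflux in other patients. This is correct, and the gap is in what is required.

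Third, earlier scans exist. All calf and thigh veins are viewed at every DUS, scans are repeated every 3–5 days in hospital, and varicose veins and edema are assessed clinically in everyone. It would be too strong to say that the blinded expert has no means of judging what is new. Yet none of these steps requires a vein-by-vein reflux record, and blinding cannot replace one.

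Fourth, the event rates and f used above are assumptions, and Section 5.5 allows a phone interview in place of a scan. Both points are accepted.

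**Conclusion.** The point holds as a mismatch between two rules that affects secondary endpoints. In patients without a DVT history, pre-existing reflux can be counted as a new venous thrombosis in the 30- and 180-day composites.

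The expected direction is inflated rates in both arms and a relative risk nearer to 1. This assumes that miscounting is equally likely in both arms, which is reasonable because the outpatient scan is blinded and the rule is common to both. The size cannot be derived from the documents; the tabulated range rests on borrowed inpatient rates and an assumed f.

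A reader might go further and conclude that the primary result or the sample size is compromised. Neither is: the primary endpoint is inpatient thrombosis on DUS, and the definitions in Section 3.5 do not use reflux. Nor do the documents suggest that the rule favours IPC.

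**What to change.** For the asymptomatic DUS component of the 30- and 180-day composites only:

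- Do not count isolated valvular insufficiency as a new thrombosis unless the same vein was recorded as competent at the primary DUS.
- Keep symptomatic thrombosis, symptomatic PE, and new obstruction or incompressibility as events. Do not make these depend on a prior record of patency. Iliac veins, for example, are scanned only on suspicion and would usually have no such record.
- Report each composite with and without reflux-only events.

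This takes a short change to Section 5.5, one line in Section 8, and a flag for reflux-only events in the data. It needs no extra procedure. The price is that a few fully recanalised thromboses showing only reflux may be missed; the with-and-without report shows how many events turn on that choice.

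If the sponsor prefers to keep reflux as a full criterion, the alternative is to record it by vein segment, with a stated threshold, at the primary DUS in all patients. That costs scanning time, including in emergency and immobile patients.
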